Templates for LNDs continue to vary based on surgeon preferences, however, a recent study examined the predictability of 5 previously identified high-risk pathologic features on lymph node metastases prior to developing surgical template for LNDs (Crispen 2008). Patients with 2 or more of the 5 criteria previously identified by Blute et al (Blute 2004) — nuclear grade 3 or 4, presence of a sarcomatoid component, tumor size ≥ 10 cm, tumor stage pT3 or pT4, and histological tumor necrosis— were considered high-risk for nodal metastases. A total of 64/169 (38%) patients had positive lymph nodes. The lymph node positivity rate was directly proportional with the number of criteria identified: 20%, 39%, 49%, and 50% for 2, 3, 4, and 5 criteria present, respectively. Lymph node spread was assessed by examining 5 different landing zones (right hilar, pre-caval, inter-aortocaval, pre-aortic, and left hilar). For right-sided tumors, 45% of positive cases had a lack of hilar region involvement. So, if only the hilar nodes (those closest to the kidney) were sampled, then 45% of positive node cases on the right would have been missed. The hilar nodes are the easiest to remove surgically during an LND and are often the only nodes removed. Intraoperative imaging of tumors can enable surgeons to visualize and perform LNDs that could result in improved clinical outcomes.

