6 ELIGIBILITY CRITERIA

6.1 Inclusion criteria for localized RCC treated with partial nephrectomy

To be considered eligible to participate in this study, a patient must meet all the inclusion criteria listed below:

- ≥ 18 years of age.
- Have primary or suspected diagnosis of RCC, with presence of cT1-2 renal mass by diagnostic CT assessment.
- Scheduled for partial nephrectomy of renal mass.
- Expected survival of at least 3 months.
- Written informed consent available.
- ECOG ≤ 1 (**Appendix G**).
- Negative serum or urine pregnancy test within 24 hours for females of child bearing age
- Recovered from toxicity of any prior therapy to \geq grade 1.

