12.3 Sample size

The study consists of a total of 20 patients divided equally between two treatment arms that will be studied simultaneously:

- Arm 1: 10- partial nephrectomy for localized RCC (no lymph nodes)
- Arm 2: 10- radical nephrectomy and lymph node dissection for locally advance or metastatic RCC.

A total sample size of 20 was determined to balance the competing goals of assessing the primary and secondary while not exposing more patients to an investigational procedure than is required. Also, there is an 88% probability of seeing at least one toxicity event if the probability of that toxicity is 0.10. Thus, we feel confident that with a sample of size 20, we will be able to detect unacceptable toxicities that have probabilities of 0.10 or higher.

A sample size of 10 for each arm was chosen. If we do not observe sensitivity for detection of RCC of at least 70% in each arm, we will consider further refinement of the methodology before proceeding with additional larger studies.

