12.7 Analysis of primary objective

The primary endpoint is to see if OTL38 and fluorescence imaging has sensitivity to detect RCC in the primary tumor (for partial nephrectomy) or in lymph nodes (for radical nephrectomy with lymph node dissection). Both sensitivity and the secondary endpoint of specificity will be assessed as follows: Final pathology and immunohistochemistry will serve as the gold standard with which gross observation and fluorescent imaging are compared for margin of resection, regional lymph nodes, and primary tumor. Pathology and immunohistochemistry results will be listed per patient. Times on and off for the imaging system will be listed per patient. Sensitivity, specificity, positive predictive value, and negative predictive value will be calculated for descriptive purposes although we understand the sample sizes are not large enough to estimate these values with a high level of accuracy at this stage. That would be accomplished in a future larger study. Sensitivity and specificity will be estimated using the method of Generalized Estimating Equations (GEE), which will take into consideration the correlated nature of multiple lesions removed from the same patient. Each patient will have all excised target lesions contributing to the data analysis (each type: O, x, ⊗, and P).

	Cancer +	Cancer-
Fluorescence+	True Positive (TP)	False Positive (FP)
Fluorescence-	False Negative (FN)	True Negative (TN)

Sensitivity (proportion of true positives) = $(TP/TP+FN) \times 100$

Specificity (proportion of true negatives) = $(TN/FP+TN) \times 100$

Sensitivity will be estimated using the GEE model for binomial distribution with fluorescence (-, +) as the fixed effect and patients as a random effect, and the 95% lower one-sided confidence interval for the true sensitivity will also be estimated. Specificity will be estimated using the GEE model for binomial distribution with fluorescence (-, +) as the fix effect and patients as a random effect, and the 95% lower one-sided confidence interval for the true specificity will also be estimated. Positive and negative predictive value will be estimated using similar methods.

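### The GEE sentences in section 12.7 condition on fluorescence, so read literally they estimate PPV and 1-NPV, not the sensitivity and specificity the section defines

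*Combined protocol and SAP*

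**What the plan says.** Section 12.7 makes sensitivity the primary quantity and specificity a secondary one. It takes final pathology and immunohistochemistry as the reference, prints a 2x2 table of fluorescence against cancer, and defines sensitivity as TP over TP plus FN and specificity as TN over FP plus TN. The inner parentheses are missing in print, but the meaning is clear.

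It then gives the estimation method:

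- Sensitivity comes from a "GEE model for binomial distribution with fluorescence (-, +) as the fixed effect and patients as a random effect", with a one-sided 95% lower limit.
- For specificity the same model is repeated: "Specificity will be estimated using the GEE model for binomial distribution with fluorescence (-, +) as the fix effect".
- For the other two measures: "Positive and negative predictive value will be estimated using similar methods".

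Neither the response nor the link is named. The section also says that these measures, down to "negative predictive value will be calculated for descriptive purposes", with limited accuracy acknowledged. Section 12.3 attaches a consequence to the primary quantity: "If we do not observe sensitivity for detection of RCC of at least 70% in each arm", refinement of the methodology will be considered before larger studies. Section 12.8 reuses the partial nephrectomy analysis for primary-tumor detection in the radical nephrectomy arm.

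**The concern.** A fixed effect is what a model conditions on. Sensitivity and specificity condition on cancer status; PPV and NPV condition on the imaging result. A model with fluorescence on the right-hand side can deliver the second pair but not the first. Section 12.7 assigns one model to all four, although they condition in two different directions.

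An analyst who programs the model sentence could therefore report a PPV and its lower limit as the primary sensitivity result, while one who follows the formula would not. PPV moves with the share of cancer among excised lesions, so the reported figure could land on either side of 70% for reasons unrelated to how well the agent detects RCC. The wording would also carry into section 12.8 and possibly into the larger studies this pilot is meant to inform.

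A smaller fault sits in the same sentence. A GEE is a marginal model with a working correlation; the patient is the cluster, and there is no patient random effect.

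**Working it through.** The plan gives no numerical result for this model to reproduce. The only probability in section 12.3, the 88% for seeing a toxicity, does reproduce (1 - 0.9^20 = 0.878) but is not an input here.

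**Inputs.** From section 12.7: the two definitions, fluorescence as covariate, binomial family, one-sided 95% lower limit. From section 12.3: 10 patients per arm and the 70% threshold. Assumed: logit link, independence working correlation, all lesion counts, and lesions allocated at random to 10 patients.

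**Step 1: what the model can estimate.** With cancer as response and one binary covariate the model is saturated. Under independence it returns the two observed proportions, whatever the link:

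- at fluorescence +: TP/(TP+FP) = PPV
- at fluorescence -: FN/(FN+TN) = 1-NPV

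Two other readings do not rescue it. If the response is agreement of fluorescence with pathology, the model gives PPV and NPV. If the data are restricted to Cancer+ lesions, the cancer response is constant.

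**Step 2: fitted models on assumed tables.**

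| TP/FN/FP/TN | Sensitivity | Literal, F+ (PPV) | Literal, F- (1-NPV) | Specificity |
|---|---|---|---|---|
| 12/3/12/53 | 12/15 = 0.800 | 12/24 = 0.500 | 3/56 = 0.054 | 53/65 = 0.815 |
| 12/8/2/58 | 12/20 = 0.600 | 12/14 = 0.857 | 8/66 = 0.121 | 58/60 = 0.967 |
| 18/2/12/48 | 18/20 = 0.900 | 18/30 = 0.600 | 2/50 = 0.040 | 48/60 = 0.800 |
| 12/3/3/62 | 12/15 = 0.800 | 12/15 = 0.800 | 3/65 = 0.046 | 62/65 = 0.954 |

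Intercept-only GEEs with fluorescence as response, fitted within Cancer+ and within Cancer- lesions, return the sensitivity and specificity columns exactly. An exchangeable working correlation changes little: for an assumed 14/6/3/27 table the literal model gives 0.829 and 0.179, against 0.824 and 0.182 under independence.

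For the first table, the one-sided lower limit varies with how lesions fall among patients. Over repeated random allocations it was about 0.25 to 0.45 for the literal model (median about 0.36) and about 0.42 to 0.71 for the corrected model (median about 0.60).

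**Step 3: dependence on cancer share p.** PPV = p·Se / [p·Se + (1-p)(1-Sp)]. The range for p is borrowed from section 3.2, where "A total of 64/169 (38%) patients had positive lymph nodes" and the rates by number of risk features were "20%, 39%, 49%, and 50% for 2, 3, 4, and 5 criteria present, respectively". These are patient-level rates, used only to set a range of 20%, 38% and 50%. With Se = 0.80:

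| Specificity | p = 0.20 | p = 0.38 | p = 0.50 |
|---|---|---|---|
| 0.70 | 40% | 62% | 73% |
| 0.80 | 50% | 71% | 80% |
| 0.90 | 67% | 83% | 89% |

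With Se exactly 0.70 and Sp 0.80, the literal model gives 0.14/0.30 = 47%, 0.266/0.390 = 68% and 0.35/0.45 = 78%. The same true sensitivity falls below the threshold twice and above it once.

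**Step 4: the limiting case in Arm 1.** Entry requires patients to "Have primary or suspected diagnosis of RCC, with presence of cT1-2 renal mass by diagnostic CT assessment", and section 12.7 targets the primary tumor. Assume one excised mass per patient. If all 10 are RCC, the literal response is constant. The fitted probability is 1.000 whether 5, 7 or 9 of 10 fluoresce (sensitivity 50%, 70%, 90%), and the intercept drifts to about 23.6 with no meaningful limit. The chance that all 10 are RCC is 0.80^10 = 11%, 0.90^10 = 35% or 0.95^10 = 60% for those assumed RCC shares.

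**The case against.** The strongest reply is that the target is not in doubt. The table and formulas are explicit, the limits are requested for the true sensitivity and specificity, and GEE is brought in only to handle several lesions per patient. A biostatistics core would probably read the model sentence as loosely worded and let the formula govern. The response is unnamed, so PPV is an inference about what would be fitted. The 70% rule speaks of what is observed, which suggests the raw proportion, and its consequence is only to consider refinement. There is no hypothesis test.

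The illustrations are also soft. The counts are invented and one table shows no error. The cancer shares are patient-level figures from a selected series. Arm 1 may contribute margin or parenchymal observations that are cancer-negative, and a constant response would show up as a failed fit.

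Most of this stands, and it limits the consequence. It does not remove the fault. No workable reading with fluorescence as covariate gives sensitivity, and the formulas alone provide no lower limit that allows for clustering. The plan asks for that limit and gives only this model to produce it. A descriptive estimate must still estimate the quantity it is named for.

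**Conclusion.** The concern holds. The definitions are right in substance, but the model sentences specify the wrong conditioning for the primary endpoint and for specificity. Taking cancer status as the unnamed response, they yield PPV and 1-NPV. That algebraic result needs no assumption about the data beyond an independence working correlation for exact equality.

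The numerical size cannot be fixed from the documents. Under the assumed tables the discrepancy runs from none to 30 points (80% to 50%, and 90% to 60%), in either direction. A change in the 70% decision is possible only if the GEE estimate, rather than the observed proportion, is the one compared; section 12.3 does not say. Because the intent can be recovered from the formulas and the study is a descriptive pilot, this is a correction to make before analysis and not a flaw in the design.

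**What to change.** Reword the model sentences in section 12.7:

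- **Sensitivity:** intercept-only binomial GEE with fluorescence-positive as the event, among Cancer+ lesions, patient as the cluster.
- **Specificity:** the same model among Cancer- lesions, with fluorescence-negative as the event.
- **PPV and NPV:** keep cancer status as response and fluorescence as covariate, for these two only.
- Replace the reference to a patient random effect with patient as the cluster, and name the link and working correlation.

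In section 12.3, state whether the observed proportion or the GEE estimate is compared with 70%.

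Add a fallback, because with a logit link the corrected model has no finite estimate or limit at 0% or 100%. With one RCC per patient and true sensitivity 0.90, 10 of 10 occurs with probability 0.90^10 = 35%. Report the exact Clopper-Pearson one-sided lower limit at patient level in that case: 0.05^(1/10) = 74.1% for 10/10. A small-sample variance correction for about 10 clusters is optional.

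The cost is wording in the statistical section; no new data, patients or procedures are needed.

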12.8 Analysis of secondary objectives

Specificity: The analysis for specificity is described above.

Detection of RCC in primary tumor (radical nephrectomy arm only): This analyses will be the same as for the primary objective in the partial nephrectomy arm. Pattern of nodal spread will be described qualitatively.

Agreement between pathological agreement between fluorescence and FR α by IHC: This endpoint will also be assessed by Kappa statistics (for presence/absence) or Intra Class Correlation (for numerical measures). Agreement between nodal and primary tumor fluorescence in the radical nephrectomy arm will be assessed similarly.

Agreement between visual and fluorescent images: Kappa statistics will be used to assess agreement between visual and fluorescent images. In addition, the number of lesions detected by

usual visible/tactile conditions and/or palpation vs fluorescent imaging will be analyzed using a paired t-test.

Inter-observer agreement: Kappa statistics will be used to assess inter-observer agreement between of captured fluorescent images.

Usefulness: Responses to the Likert scale questionnaire completed by the surgeons will be listed and summarized

Safety: Vital signs will be summarized using descriptive statistics. Clinical chemistry, hematology, and urinalysis laboratory values will be listed in tabular format and those with above or below normal range will be identified within the table. AEs and TEAEs will be summarized by body system and presented by severity and causal relationship to study drug. ADEs will be summarized by body system and presented by severity and causal relationship to study device. Patients experiencing serious AEs or serious ADEs will be listed and summarized in tabular format.

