To further assess agreement of gross fluorescence with pathology, at least one representative lymph node biopsy done. Once the specimen is removed, it will be processed by the surgical team on the back table and sent to pathology for microscopic examination and immunohistochemistry assessment to determine if it contains FR α + cancer cells. The pathologist will be blinded to the fluorescence results of the tumor.

For All Surgeries

- Vital signs: recorded per institutional practice
- AE assessment: including hypersensitivity reactions, which could include skin reactions, difficulty breathing, eye or nasal reactions, or gastrointestinal complaints, redness, tenderness, pain, or rash at the injection site or any clinically relevant abnormality (with exception of surgical scars) that was not present at screening.
- Adverse device effects (ADE) assessment: the surgeon will examine the subject to confirm that there are no visible changes to skin (erythema or pigment darkening), tissue or organs related to fluorescence. Changes could be present but are likely due to the temperature of the cauterization as lesions are excised.
- Concomitant medications: record all intraoperative medications (this does not include normal saline or other routine maintenance intravenous fluids)

8.3.2.3 Post-surgery:

- Post-surgery questionnaire: the surgeon will complete a questionnaire describing the usefulness of the fluorescence imaging for tumor removal and to achieve a negative margin (**Appendix A**).
- Blinded surgeon assessment: A co-investigator, blinded surgeon who was not involved with the case will view the photographs and complete a questionnaire to assess inter-observer agreement (**Appendix A**).
- Type of RCC excision (radical, partial), need for blood transfusion and estimated blood loss
- Vital signs: recorded per institutional practice

- AE assessment: including hypersensitivity reactions, which could include skin reactions, difficulty breathing, eye or nasal reactions, or gastrointestinal complaints, redness, tenderness, pain, or rash at the injection site or any clinically relevant abnormality (with exception of surgical scars) that was not present at screening.
- ADE assessment: the surgeon will examine the subject to confirm that there are no visible changes to skin (erythema or pigment darkening), tissue or organs related to fluorescence.

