19.1.1 Partial nephrectomy

Intraoperative surgeon assessment tool

Primary surgeon questionnaire: fill out immediately following completion of case.

1. What camera was used during the case?
 - a. da Vinci® Fluorescence Imaging Vision System
 - b. Visionsense VSiii 3DHD

2. At what time was the fluorescent camera first used during the case?
 - a. _____

3. List all organs or structures with fluorescence:
 - a. _____

4. Does the tumor show fluorescence?
 - a. Very bright fluorescence
 - b. Bright fluorescence
 - c. Mild fluorescence
 - d. Minimal fluorescence
 - e. No fluorescence

5. Does the normal kidney surrounding the tumor show fluorescence?
 - a. Very bright fluorescence
 - b. Bright fluorescence
 - c. Mild fluorescence
 - d. Minimal fluorescence
 - e. No fluorescence

6. Compare fluorescence between tumor and kidney:
 - a. Tumor is a lot more than the kidney
 - b. Tumor is more than the kidney
 - c. Tumor is the same as the kidney
 - d. Tumor is less than the kidney
 - e. Tumor is a lot less than the kidney

7. Does fluorescence aid in locating the renal tumor?
 - a. Yes, a lot
 - b. Yes, somewhat
 - c. Not sure
 - d. No, somewhat worse than without fluorescence
 - e. No, a lot worse than without fluorescence

8. Does fluorescence help resect the tumor?
 - a. Yes, a lot
 - b. Yes, somewhat
 - c. Not sure
 - d. No, somewhat worse than without fluorescence
 - e. No, a lot worse than without fluorescence

9. Does fluorescence help to identify the border or margin of the tumor during resection?
 - a. Yes, a lot
 - b. Yes, somewhat
 - c. Not sure
 - d. No, somewhat worse than without fluorescence
 - e. No, a lot worse than without fluorescence

10. If commercially available would you use this fluorescent product for partial nephrectomies?
 - a. Yes, a lot
 - b. Yes, somewhat
 - c. Not sure
 - d. No, most likely not
 - e. No, for sure not

11. Based on white light examination after tumor removal, are there any visible changes to organs (erythema or pigment change)?
 - a. Yes, explain _____
 - b. No

12. Based on white light examination after tumor removal are there any visible changes to skin (erythema or pigment darkening)?
 - a. Yes, explain _____
 - b. No

Blinded surgeon assessment of intraoperative photos

To be completed by surgeons not involved in case

1. Photographs taken with and without fluorescent imaging just inside trocar showing hemi-abdomen: Gerotas, colon, and liver (right); colon, spleen, stomach (left).

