 - a. Place “X” over any fluorescing regions and draw outline of each fluorescing area
 - b. Place “O” on white light images over tumor areas and draw outline of suspected tumor.
2. Photographs with and without fluorescent imaging taken after Gerotas removed showing tumor and surrounding normal parenchyma.
 - a. Place “X” over any fluorescing regions and draw outline of each fluorescing area
 - b. Place “O” on white light images over tumor areas and draw outline of suspected tumor.
3. Photographs with and without fluorescent imaging taken during resection of tumor.
 - a. Place “X” over any fluorescing regions
 - b. Place “O” on white light images over tumor areas
4. Photographs with and without fluorescent imaging taken in tumor fossa after tumor removal.
 - a. Place “X” over any fluorescing regions and draw outline of each fluorescing area
 - b. Place “O” on white light images over tumor areas and draw outline of suspected tumor.

Ex-vivo assessment of removed tumor

Primary surgeon to complete on back table immediately following case. All images are in digital full color.

1. What camera was used for ex-vivo assessment?
 - a. da Vinci® Fluorescence Imaging Vision System
 - b. Visionsense VSiii 3DHD
2. Gross fluorescent images of specimen 90° from each other by rotating about central axis. Also, upper and lower pole images (6 faces of specimen).
3. Does the tumor show fluorescence?
 - a. Very bright fluorescence
 - b. Bright fluorescence
 - c. Mild fluorescence
 - d. Minimal fluorescence
 - e. No fluorescence
4. 5mm slices through specimen with both fluorescent and white light image of each slice. Calibration measurement in photo.
5. At least 1 representative sample will be sent of primary tumor for FR- α assessment

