The Positive Pixel Count algorithm was used to quantify the amount of a specific stain present in a scanned slide image. The Positive Pixel Algorithm was altered with a hue value of 0.62, hue width of 0.40, and color saturation threshold of 0.005. A spectrum of color (range of hues and saturation) and intensity (weak, positive, and strong) were masked and evaluated. The algorithm counted the number and intensity-sum in each intensity range, along with three additional quantities: average intensity, ratio of strong/total number, and average intensity of weak positive pixels. Only staining classified as “positive” or “strong positive” was used to calculate positivity; regions classified as “weak positive” were mostly cytoplasmic and background staining, and were not counted. The algorithm had a set of default input parameters when first selected—these inputs have been pre-configured for Brown color quantification in the three intensity ranges (220-175, 175-100, and 100-0). Pixels which were stained, but did not fall into the positive-color specification, were considered negative stained pixels—these pixels were counted as well, so that the fraction of positive to total stained pixels could be determined. The ratio of the ‘Positive’ and ‘Strong Positive’ to the total number of pixels provided the positivity percentage for each sample. The algorithm was applied to an image using ImageScope. This program allows for the selection of an image Region of Analysis and the specification of input parameters. After this is completed, the algorithm can be applied and the results can be viewed.

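### Intraclass correlation between fluorescence brightness and FRα pixel positivity would reflect units and coding rather than concordance; use a rank correlation and write down both binary rules for kappa

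*Combined protocol and SAP*

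**What the plan says.** Section 12.8 compares fluorescence with FRα by "Kappa statistics (for presence/absence) or Intra Class Correlation (for numerical measures". It does not say which measures count as numerical, which form of ICC is meant, whether anything is rescaled, or when each statistic applies.

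The data that could feed it are described elsewhere:

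- **Fluorescence.** Appendix A (19.1.1 and 19.1.2) asks "Does the tumor show fluorescence", with five ordered verbal answers from very bright to none. No numeric code is attached. Section 12.7 also treats fluorescence as -/+.
- **IHC, quantified.** In Appendix B (19.2), the ratio of positive and strong positive pixels "to the total number of pixels provided the positivity percentage for each sample". The rule there concerns pixels: "regions classified as “weak positive” were mostly cytoplasmic and background staining, and were not counted". No percentage is given at which a sample counts as FRα positive.
- **IHC, binary.** Section 8.3.2.2, in its radical nephrectomy part, has a pathologist blinded to fluorescence make an "immunohistochemistry assessment to determine if it contains FR α + cancer cells". No threshold is written.
- **Number of samples.** Appendix A: "At least 1 representative sample will be sent of primary tumor for" FRα assessment. Section 12.3: "The study consists of a total of 20 patients divided equally between two treatment arms", so 10 per arm.

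**The concern.** ICC treats its two columns as interchangeable readings of one quantity in one unit. A five-step brightness category and a percentage of stained pixels are not such readings. If they are paired, the gap between the two means and the ratio of the two spreads enter the statistic directly. Those reflect how the data were entered and how widely staining happened to vary.

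Agreement of fluorescence with FRα is a secondary endpoint in both arms (Section 12.4) and checks whether the OTL38 signal follows its target. Section 3.3 says the pilot data will help develop larger protocols. A value that changes size, or even sign, with a coding choice could misinform that step.

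**Working it through.** The plan gives no figure for this analysis, so there is nothing to reproduce first. The check uses constructed data in which concordance is perfect by design.

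**Assumed inputs.** Ten samples (one arm, one sample per patient); brightness coded 1 = none to 5 = very bright, two samples per level; IHC an exact straight line in the score, IHC = a + b × score. Spearman is therefore 1.00. The coding and the IHC ranges are assumptions; the documents give neither.

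**Formulas.** Let s1² and s2² be the two variances, c the covariance, d the difference in means (IHC minus score), n the number of samples, and V = s1² + s2² - 2c.

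- ICC, consistency = 2c / (s1² + s2²)
- ICC, absolute agreement = 2c / (s1² + s2² + d² - V/n)

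The score has mean 3 and variance 20/9 = 2.222. Hence s2² = b² × 2.222, c = b × 2.222, and consistency reduces to 2b/(1 + b²).

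**Worked case, IHC 10, 30, 50, 70, 90%.** b = 20, d = 50 - 3 = 47, c = 44.44, s1² + s2² = 891.11, V = 19² × 2.222 = 802.22.

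- Consistency = 88.89 / 891.11 = 0.10
- Absolute agreement = 88.89 / (891.11 + 2209 - 80.22) = 88.89 / 3019.89 = 0.03
- The one-way form gives -0.50

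**The same perfect concordance under other entries (n = 10):**

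| IHC values and coding | b | d | Absolute | Consistency |
|---|---|---|---|---|
| 10-90% | 20 | 47 | 0.03 | 0.10 |
| 0-20% | 5 | 7 | 0.22 | 0.38 |
| 0-10% | 2.5 | 2 | 0.57 | 0.69 |
| 0.10-0.90, as a fraction | 0.2 | -2.5 | 0.11 | 0.38 |
| 10-90%, very bright coded 1 | -20 | 47 | -0.03 | -0.10 |
| IHC mapped to 1-5 | 1 | 0 | 1.00 | 1.00 |

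Spearman is 1.00 in every row except the reverse-coded one. There it is -1.00, with the same strength and only the sign reversed.

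**Comparison with no association.** For IHC spread over 0-100%, perfect concordance gives 0.03 (absolute) and 0.08 (consistency), at n = 10 and at n = 20. In 5,000 random re-pairings of the same values (n = 10), the central 95% of results was -0.02 to 0.02 and -0.05 to 0.05. A larger sample does not cure the problem.

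**Kappa.** Kappa = (po - pe)/(1 - pe). Take the 10-90% data and call fluorescence present if minimal or brighter (8 of 10 samples).

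- IHC cut 20%: 8 positive, complete agreement, kappa 1.00
- Cut 40%: 6 positive, po = 0.80, pe = 0.8 × 0.6 + 0.2 × 0.4 = 0.56, kappa = 0.24/0.44 = 0.55
- Cut 60%: 4 positive, po = 0.60, pe = 0.44, kappa = 0.16/0.56 = 0.29
- Cut 80%: 2 positive, po = 0.40, pe = 0.32, kappa = 0.08/0.68 = 0.12

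Kappa can be computed, but its value depends on the binary rules, and neither is written.

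**Could an ROC area be used?** It needs fluorescence-negative samples. Assume one sample per patient and that fluorescence-negative means FR-negative. Section 5.1.1.2 mentions 5-10% of patients; Section 3.3 has FRα upregulated in up to 75%, so take 25% negative. The chance of no negative among 10 is 0.95^10 = 60%, 0.90^10 = 35% and 0.75^10 = 6% respectively.

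**The case against.** The strongest reply is that the invalid pairing is inferred. Section 12.8 names no measures, and the 1 to 5 scores appear nowhere. Other fluorescence data exist: lesion counts and locations (Section 8.3.2.2), outlined areas and calibrated slice images (Appendix A). Counts of fluorescent and of FRα-positive lesions would share a unit. That stands, and it is why the point is conditional on the natural pairing. But no numerical summary of the outlines or images is defined, and FRα testing is assured for only one sample of the primary tumor per patient, so matched counts are not assured either.

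A reader might infer that ICC always reads near zero here. It does not: a 0-10% spread gives 0.57/0.69, and a common scale gives 1.00. The fault is dependence on units and spread.

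A reader might also infer that kappa fails too, leaving no workable analysis. The documents do not support that. The blinded pathologist's FRα call and the -/+ fluorescence reading supply two binary variables without any pixel percentage. What is missing is a written rule for each. Section 8.3.2.2 also mentions a study pathology manual that is not included and may hold one for IHC.

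Finally, ICC is not the only readout: Section 12.7 lists IHC results per patient and uses pathology and IHC as the reference for sensitivity and specificity. That limits the harm.

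**Conclusion.** The point holds in a conditional form. If ICC is applied to brightness category and positive-pixel percentage, which is the natural reading of Section 12.8 with Appendices A and B, the result does not measure concordance. Under perfect rank concordance it ran from -0.03 to 0.57 for absolute agreement and from -0.10 to 0.69 for consistency across the mismatched entries shown. These figures rest on an assumed coding, assumed IHC ranges and ten constructed samples; they illustrate the fault and do not predict the trial's result.

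Comparing nodal with primary tumor fluorescence uses one brightness scale, so the unit mismatch does not arise there. The consequence is confined to the interpretability of one descriptive secondary endpoint in a 20-patient pilot. No sample size or error rate depends on it.

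**What to change.** In Section 12.8:

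1. For fluorescence versus FRα, replace ICC with Spearman or Kendall tau-b between brightness category and positivity percentage, with the coding direction stated. Describe the result as association.
2. Keep ICC only where both readings are on one scale.
3. Keep kappa for presence/absence, from the blinded pathologist's FRα call and the fluorescence -/+ call. Write the rule for each call before the two sets of results are linked, and say that the pathologist's call applies in both arms, since Section 8.3.2.2 describes it only under radical nephrectomy.
4. An ROC area of positivity percentage is optional: only with a prespecified level for fluorescence-positive, and only if fluorescence-negative samples occur.

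The cost is a few sentences and two written rules, with no new data. Section 12 allows changes to the analysis without an amendment unless a significant feature of the protocol changes. The small downside is that a rank correlation measures association, whereas the objective is worded as agreement; kappa continues to address agreement.
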